- 3) VAP caused by a MDR pathogen: Early VAP is rarely caused by MDR pathogens; in a recent analysis of our surgical ICU, 94% of cases of early VAP were caused by highly sensitive pathogens (Methicillin-sensitive staphylococcus aureus 39%, Haemophilus influenza 35%, Streptococcus pneumoniae 16%, Esterichia coli 9%) [14]. Patients with early VAP caused by the following MDR pathogens will be excluded: Methicillin-resistant Staphylococcus aureus (MRSA), Vancomycin-intermediate Staphylococcus aureus (VISA), pseudomonas aeruginosa, Vancomycin-resistant enterococcus (VRE), Acinetobacter baumannii, Stenotrophomonas maltophilia, carbapenem-

resistant enterobacteriaceae (CRE), and extended-spectrum beta lactamase producing gram negative bacilli.

- 4) Causative pathogen not sensitive to choice of initial empiric antibiotic.
- 5) Antibiotic therapy for ≥ 5 of the last 10 days preceding the BAL.
- 6) Septic shock, defined as evidence of tissue hypoperfusion after adequate volume expansion, due to infection, and requiring ≥ 1 vasopressor [17].
- 7) Current or recent (within 30 days) use of immunosuppressive medications.
- 8) Length of stay ≥ 72 hours in a transferring facility.
- 9) Pregnancy or lactation.
- 10) Legal arrest or incarceration.
- 11) Moribund state in which death is imminent.

Outcomes:

The two main outcomes will be effectiveness of treatment and antibiotic exposure.

Effectiveness of treatment will be assessed in three ways: 1) Clinical response, 2) MR, and 3) biomarker response.

Clinical Response: Current guidelines state that appropriately treated patients with VAP should have a favorable clinical response by day 3, and a substantial improvement by day 6 [9]. Clinical variables used to assess for treatment response are organized into the Clinical Pulmonary Infection Score (CPIS). The original CPIS, as described by Pugin et al. [18], included five clinical variables [temperature, white blood

cell count (WBC), tracheal secretions, ratio of P_aO_2 to F_iO_2 (P:F), and chest radiograph findings) and one microbiologic variable (culture of tracheal aspirate and its relationship to the gram stain). Several authors have since modified the score to exclude the microbiologic variable in order to both screen for VAP and monitor efficacy of treatment [11, 19]. This modified score, herein referred to as CPIS_{clinical}, omits the microbiologic variable and ranges from 0-10.

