Currently, procalcitonin concentration is measured in all surgical ICU patients for whom a BAL is sent on the day of the BAL as part of a separate non-interventional study. For the purposes of the current trial, procalcitonin concentration will also be measured during treatment in order to assess response, as well as following treatment in order to assess for recurrence. Because study entry will occur at the time that VAP is confirmed microbiologically (approximately 72 hours following the BAL and initiation of empiric antibiotics), these measurements will begin after three days of antibiotic therapy. Procalcitonin concentration will then be measured daily for the remainder of treatment, as well as daily for 72 hours following treatment. Thus, the 4 day group will have procalcitonin concentration measured at baseline, treatment days 3 and 4, and post treatment days 1-3. The 8 day group will have procalcitonin measured at baseline, treatment days 3-8, and post-treatment days 1-3. The treatment team will have access to the results of these measurements. For the purposes of the trial, biomarker resolution will be defined as a procalcitonin concentration $< 0.5 \mu\text{g/L}$ or a decrease of $\geq 80\%$ relative to the day of the BAL [26].

Additional Outcomes: Days of antibiotics, antibiotic days (defined as the product of days of antibiotics and number of antibiotics per day), recurrence, ventilator days, empyema, need for tracheostomy, non-pulmonary infections, ICU length of stay (LOS), hospital LOS, and mortality. Recurrence is defined using the same clinical and microbiologic criteria as the initial episode of VAP, and occurring 2-14 days

following completion of initial therapy. Relapse is defined as recurrent VAP caused by the initial pathogen; super-infection is defined as recurrent VAP caused by ≥ 1 new pathogen. VAP occurring > 14 days following completion of initial therapy will be considered a second episode of pneumonia as opposed to a recurrence. The incidence of recurrent VAP due to a MDR pathogen, as well as any other infection caused by a MDR pathogen, will also be abstracted.

Baseline Variables: Age (years), gender, admission diagnosis, associated diagnoses, admission APACHE II score, comorbidity index [27], prior and current antibiotic exposure, base deficit, serum lactate concentration, time from ICU admission to BAL, presence of organisms on gram stain, and presence of polymorphonuclear lymphocytes on gram stain.

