Sample acquisition and processing: The default method for BAL specimen acquisition will be via the blind or “mini” BAL technique [18], using an 85 mm by 4 mm bronchial diagnostic catheter (Combicath, ® Prodimed, Neuilly-en-Thelle, France). The catheter is passed through the artificial airway until resistance is met. It is then withdrawn approximately 1 cm and the inner lavage catheter is deployed. Lavage is then performed with 20 – 40 mL of sterile saline.

The BAL will be obtained bronchoscopically if bronchoscopy is being performed for another indication (e.g., pulmonary toilet, percutaneous dilational tracheostomy). Lavage is performed using 20-40 mL of normal saline lavage into the lobar bronchus that appears most abnormal on CXR.

Using a 0.001 calibrated loop, vortexed BAL specimens will be plated onto sheep blood, MacConkey, and Chocolate agar at 35°C - 37°C in CO₂. Plates will be examined after 24, 48, and 72 hours prior to issuing a final negative report. 100 or more colonies per plate is considered significant and represents $\geq 10^5$ cfu/mL.

Statistical Analyses:

Power analysis: Power analysis was performed using SAS Version 9.1 (SAS, Inc., Carey, NC, *proc power*). The Analysis was based on a non-inferiority study design, defined as a difference in outcomes between the 4 day and 8 day groups of < 10%. Furthermore, as the intention was to show non-inferiority, tests were one-sided using an alpha error level of 0.10. The beta error level was set at 0.20 for 80% power. Analysis for the outcome of VAP recurrence returned the largest sample size. From 2010-2012, during which time VAP was treated with ≥ 8 days of therapy, the incidence of recurrent VAP in the DHMC surgical ICU was approximately 25%. Projecting a recurrence rate after 4 days of treatment of 35% returns a total sample size of 103..

Interim Analysis: An interim analysis will be conducted for all outcomes after 50% accrual (n_{total}=50).

Data Analysis: Data analyses will be performed using SAS Version 9.1 (SAS, Inc., Carey, NC). Data will be analyzed using an intention-to-treat strategy (i.e., patients randomized to receive 4 days of antibiotic therapy will be analyzed with this group even if they receive longer courses). Data will be expressed as median (range) or number (%). Normality of continuous variables will be assessed using the

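### No rule says which effectiveness result decides the trial, and the outcome that set the sample size, VAP recurrence, is listed only as an additional outcome

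*Combined protocol and SAP*

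**What the plan says.** Four places in the combined protocol and SAP bear on this.

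- **Outcomes.** "The two main outcomes will be effectiveness of treatment and antibiotic exposure". Then: "Effectiveness of treatment will be assessed in three ways: 1) Clinical response, 2) MR, and 3) biomarker response". The three are not ordered, and nothing says whether one, two or all three must be favourable. The clinical measure, a 0 to 10 score, is given no cut-off for response. The text on clinical response concedes that this score has limited accuracy in surgical ICU patients and says that efficacy will therefore also be judged microbiologically and by biomarker.
- **Additional Outcomes.** Recurrence appears here: "Additional Outcomes: Days of antibiotics, antibiotic days (defined as the product of days of antibiotics and number of antibiotics per day), recurrence, ventilator days". Two different measures of antibiotic exposure are in the same list.
- **Power analysis.** "Analysis for the outcome of VAP recurrence returned the largest sample size". The total of 103 is derived from recurrence of 25% after 8 days and 35% after 4 days. Non-inferiority is "defined as a difference in outcomes between the 4 day and 8 day groups of < 10" percent, applied to outcomes in general, and "tests were one-sided using an alpha error level of 0.10". Power is 80%.
- **Data Analysis.** Difference tests are listed with an alpha of 0.05 for everything. There is no primary outcome, order of testing, multiplicity rule or non-inferiority decision rule. The Interim Analysis paragraph adds a look at all outcomes at 50 patients.

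**The concern.** The hypothesis has two parts: that 4 days is as effective as 8, and that it reduces antibiotic exposure. A reader of the results must know which finding settles the first part. The plan offers three candidates of equal standing and a fourth outcome, recurrence, that carries the sample size but not the status. If the measures disagree, the choice among them could be made after the results are known. The effectiveness conclusion could not then be read as a confirmatory test with a known error rate, and the sample-size justification would belong to a different outcome from the one on which the claim is made.

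**Working it through.** **1. The plan's own figure.** Inputs from the power analysis: 25% and 35% recurrence, 10-point margin (absolute scale assumed), one-sided alpha 0.10, power 80%. Allocation is not stated; 1:1 is assumed. (z0.90 + z0.80)² = (1.2816 + 0.8416)² = 4.508.

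- Detecting 25% against 35% with a pooled two-proportion test: 189 per arm, 378 in total.
- Non-inferiority with 25% in both arms: 4.508 × 2 × 0.25 × 0.75 / 0.10² = 169.05, so 170 per arm, 340 in total.
- Non-inferiority with a true 35% against 25%: the assumed difference equals the margin, so no sample size gives 80% power.
- A one-sample formula, 4.508 × 0.35 × 0.65 / 0.10² = 102.6, rounds to 103. This is only a numerical match and does not show how the figure was obtained.

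So 103 is not reproduced by a two-arm formula from the stated inputs.

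**2. Power for recurrence at 103 patients.** With 51.5 per arm and 25% in both arms, the standard error of the difference is √(2 × 0.25 × 0.75 / 51.5) = 0.0853, and 0.10 / 0.0853 = 1.172.

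- One-sided 0.10: Φ(1.172 − 1.282) = Φ(−0.110) = 46%.
- One-sided 0.05: Φ(1.172 − 1.645) = Φ(−0.473) = 32%.
- True 25% against 35%: the truth lies on the margin, so power equals alpha.
- For 80% power with 25% in both arms: 340 in total at 0.10, 464 at 0.05.

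**3. Error rate if any one of three measures sufficed.** Assumptions: each measure is a one-sided non-inferiority test, each true difference lies exactly at its margin, and the test statistics are equally correlated normals. With independence the rate is 1 − (1 − α)³. Correlated values are from simulation.

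| Correlation | α = 0.10 each | α = 0.05 each |
|---|---|---|
| 0 | 1 − 0.90³ = 27.1% | 1 − 0.95³ = 14.3% |
| 0.5 | about 22% | about 12% |
| 0.9 | about 15% | about 8% |

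**4. If all three had to succeed.** The error rate cannot exceed α, but power falls. For illustration, three independent tests with 80% power each succeed together with probability 0.8³ = 51%.

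**5. Whether the largest sample size covers the named measures.** No rates or sample sizes are given for them. Under the same 10-point margin, one-sided 0.10 and 80% power, with equal true rates, an outcome near 50% needs 452 in total and one near 5% or 95% needs 86, against 340 for recurrence at 25%. The answer turns on rates the document does not give.

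**The case against.** The strongest defence has four parts.

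First, a reader might infer that the trial was not sized for its main effectiveness measures. The text does not support that. Saying that recurrence gave the largest number implies that other outcomes were calculated too, and sizing on the most demanding outcome is a recognised approach. What stands is that the calculations are not shown, so their adequacy cannot be checked.

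Second, a reader might infer that success on any single measure is enough, perhaps with recurrence as a further route. The plan says neither. Its remark that efficacy will also be judged microbiologically and by biomarker can be read as corroboration. The error rates above are therefore conditional. Independence is also unlikely, because the protocol itself cites a correlation between procalcitonin normalisation and clinical response. The lower end of the range deserves weight, though even at correlation 0.9 the rate is about one and a half times nominal.

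Third, the rates describe tests that the plan does not define: the clinical score has no response cut-off, and Data Analysis lists no non-inferiority test. That is fair, but it adds to the gap in the decision rule.

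Fourth, choosing recurrence is a preference. The protocol argues for a microbiologic endpoint, and naming one response measure or requiring all three would also close the gap. This is true. Recurrence is suggested because the plan's own sample size uses it and because its criteria and time window are stated. Making it primary is nevertheless more than a change of label, given the power in step 2.

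**Conclusion.** The concern holds in this form: effectiveness rests on three unranked measures with no rule for which result, or how many, decides; the outcome that set the sample size has only additional status; all testing is at p<0.05 with no hierarchy; and the sizing of the three named measures is undocumented. Adding a procedural detail would not cure this, because following the plan as written leaves the effectiveness claim open to selection among results.

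The size depends on the rule eventually applied. Any one of three gives a false-claim rate of about 15% to 27% at one-sided 0.10 each, or 8% to 14% at 0.05, under the assumptions in step 3. All three gives no inflation and lower power. The documents do not show that the permissive rule was intended, nor that the named measures were left out of the sizing. Effectiveness is also one of two main outcomes, so the point concerns that half of the hypothesis.

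**What to change.** Before any interim or unblinded look, amend Outcomes and Statistical Analyses as follows.

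1. Make VAP recurrence the single primary effectiveness outcome. Test non-inferiority by comparing the confidence limit for the risk difference (4 days minus 8 days) with the stated 10-point margin, at one stated one-sided alpha. This means reconciling 0.10 in the power analysis with 0.05 in Data Analysis.
2. Name one antibiotic-exposure measure from the two now listed and test it for superiority. The hypothesis requires both results, so no alpha split is needed.
3. Report clinical, microbiologic and biomarker response as secondary, as differences with confidence intervals and no non-inferiority claim.
4. Restate the sample size and power for the primary test, with the assumed true rates shown.

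The first three steps need changes to the protocol text and registration. The sponsor gives up effectiveness claims on the other measures. The larger cost is the fourth step: 103 patients give about 46% power (one-sided 0.10) or 32% (0.05) with 25% recurrence in both arms, and only alpha under the projected 25% against 35%. The sponsor must enlarge the trial or state openly that the primary test is underpowered. Follow-up stops at hospital discharge, while recurrence is counted from 2 to 14 days after therapy, so the amendment should also say how patients discharged before that window closes are handled.

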One subset of patients for whom a decreased duration of antimicrobial therapy may be particularly effective is those who develop VAP \leq 7 days after intubation (early VAP). Early VAP comprises the majority of cases of pneumonia diagnosed in the ICU[14] . Furthermore, as compared to patients who develop late VAP, patients who develop early VAP are more likely to be infected with community-acquired pathogens sensitive to narrow spectrum antibiotics [14]. Finally, nearly all cases of

early VAP caused by sensitive pathogens demonstrate MR after relatively short (3-5 days) courses of therapy [10].

The hypothesis of this randomized clinical trial (RCT) is that 4 days of antibiotic therapy, as compared to 8 days, is equally effective and results in decreased antibiotic exposure among surgical ICU patients with early VAP.

Methods:

Study Design: Randomized, double-blind (until treatment day 5) clinical trial.

Intervention: Default 4 vs. 8 days of antibiotic therapy.

Screening Pool: Trauma-Surgical ICUs.

Inclusion Criteria:

- 1) Surgical patient
- 2) Early VAP, defined as:
 - a. Duration of Intubation: 2-7 days [9] (via endotracheal or tracheostomy tube).

- b. Clinical suspicion of pneumonia: New or progressing infiltrate on chest radiograph (CXR) along with ≥ 1 of the following: Temperature $\geq 38.5^{\circ}\text{C}$ or $< 36.5^{\circ}\text{C}$; blood leukocytes $>11,000 \text{ mm}^3$ or $<4,000 \text{ mm}^3$; purulent tracheal secretions; or $\text{PaO}_2:\text{FiO}_2 < 200$ [15].
- c. Quantitative microbiologic confirmation: Bronchoalveolar lavage (BAL) culture showing $\geq 10^5 \text{ cfu/mL}$ of at least one pathogen [16]. The quantitative microbiology threshold will be lowered to $\geq 10^4 \text{ cfu/mL}$ if the patient was being treated with antibiotics to which the pathogen is sensitive at the time of the BAL.

3) Hospital LOS ≤ 10 days at the time that the BAL was obtained.

Exclusion Criteria:

- 1) Age < 18 years.
- 2) Prior episode of VAP for the index admission (the patient may have had prior BALs sent for culture, but these cannot have met the above mentioned diagnostic criteria for VAP).

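### The total of 103 does not give 80% power for the 10-point non-inferiority comparison of VAP recurrence: power is about 46% if both true rates are 25%, and 10% under the projected 25% versus 35%

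*Combined protocol and SAP*

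**What the plan says.** The trial randomizes patients to two groups (Methods, Intervention: "Intervention: Default 4 vs. 8 days of antibiotic therapy"). Under Statistical Analyses, Power analysis, the design is non-inferiority, "defined as a difference in outcomes between the 4 day and 8 day groups of < 10" percent, and "tests were one-sided using an alpha error level of 0.10". On power: "The beta error level was set at 0.20 for 80% power".

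Recurrence determines the trial's size: "Analysis for the outcome of VAP recurrence returned the largest sample size". For the 8-day arm the plan uses local data from 2010–2012, when "the incidence of recurrent VAP in the DHMC surgical ICU was approximately 25" percent. The calculation ends: "Projecting a recurrence rate after 4 days of treatment of 35% returns a total sample size of 103".

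The figure is for both arms together. The text calls it a total, and the Interim Analysis paragraph puts 50% accrual at 50 patients in total. No formula, allocation ratio or dropout allowance is given; only the SAS power procedure is named.

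**The concern.** A non-inferiority trial is normally powered at a true difference smaller than the margin, most often zero. Here the projected difference equals the margin, and at that point power cannot exceed the type I error rate. Separately, about 51 patients per arm is very few for a 10-point margin on an event rate near 25%, even at one-sided alpha 0.10.

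The trial's hypothesis is that 4 days is as effective as 8. If the stated 80% is really under one half, failure to show non-inferiority is the likelier result even when the hypothesis is true. An inconclusive result could then be read as evidence against the shorter course. Equally, a non-significant chi-squared test could be read as evidence of equivalence.

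**Working it through.** **Inputs from the Power analysis paragraph.** 8-day recurrence 25%; 4-day recurrence 35%; margin 10 points; one-sided alpha 0.10 (z = 1.2816); power 80% (z = 0.8416); total 103. Then (1.2816 + 0.8416)² = 2.1232² = 4.508.

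**Assumptions added here.** 1:1 allocation (51.5 per arm), no dropout, and a normal-approximation (Wald) test on the risk difference with unpooled variance. The plan specifies none of these.

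**1. Reproducing 103.** A one-sample formula with the variance taken at 35% gives

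n = 4.508 × 0.35 × 0.65 / 0.10² = 102.55, rounded up to 103.

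This compares one group with a fixed rate. It gives the other arm no sampling error.

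**2. Two-arm formulas with the stated alpha, power and 10 points.**

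| Reading | Per arm | Total |
|---|---|---|
| Non-inferiority, 25% in both arms: 4.508 × 2 × 0.25 × 0.75 / 0.10² = 169.04 | 170 | 340 |
| Non-inferiority, 30% in both arms | 190 | 380 |
| Non-inferiority, 35% in both arms | 206 | 412 |
| Detecting 25% vs 35%, unpooled: 4.508 × (0.1875 + 0.2275) / 0.10² = 187.1 | 188 | 376 |
| Detecting 25% vs 35%, pooled null variance (188.4) | 189 | 378 |

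Entering the 10-point difference in favour of 4 days gives about 94 in total. None of these gives 103.

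**3. Power at 103 in total, true rates 25% and 25%.**

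SE = √(2 × 0.25 × 0.75 / 51.5) = 0.0853

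Power = Φ(0.10 / 0.0853 − 1.2816) = Φ(1.172 − 1.282) = Φ(−0.110) = 45.6%

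Exact enumeration of the same test gives 45.8% or 47.0%, depending on which arm has 52 patients.

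**4. Power at 103 in total, true rates 25% and 35%.** The distance to the margin is 0.10 − 0.10 = 0, so power = Φ(0 − 1.2816) = 10.0% (exact 10.1% to 10.3%). Because the numerator is zero, the sample size drops out and no finite N reaches 80%.

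**5. Sensitivity.**

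| Scenario | Power |
|---|---|
| 25% vs 30% (8 vs 4 days) | 23.8% |
| 15% in both arms | 56% |
| 35% in both arms | 41% |
| 25% vs 20%, 4 days truly better | 71% |
| 103 per arm, against the text, 25% in both arms | 65% |
| 103 total, 25% in both arms, judged by a two-sided 95% CI: Φ(1.172 − 1.960) | 22% |

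**6. Margin that 103 supports.** With 25% in both arms, 80% power needs a margin of 2.1232 × 0.0853 = 0.181, about 18 points.

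**The case against.** The best case for the plan has four parts.

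- **The source of 103 is inferred.** The plan names only the SAS procedure. Other one-sample versions on the same inputs give about 85, 91 or 95. A two-arm formula with a 20-point margin at a common 35% rate has the same algebra: 51.28 per arm, 102.55 in total before rounding. This stands. The match shows where the number may have come from and does not prove it. The power shortfall does not depend on the explanation, because the plan states 10 points.
- **The 46% uses a scenario that the plan does not state.** Its only 4-day rate is 35%, and the authors may have meant that figure as 25% plus the margin. This is also fair. Equal rates follow from the hypothesis of equal effectiveness, and they are the more generous of the two readings. The literal reading gives 10%.
- **Recurrence is listed under Additional Outcomes.** The two main outcomes are effectiveness of treatment (clinical, microbiologic and biomarker response) and antibiotic exposure, and power differs by event rate. With a 5% rate in both arms, 103 patients give about 85% power for a 10-point margin. So the 46% and the 18 points apply to recurrence near 25% only. Even so, recurrence is the outcome that the plan says set the sample size.
- **No non-inferiority test or interval is specified in the Data Analysis paragraph.** The 22% is therefore conditional on judging the margin by a two-sided 95% interval. The conflict between alpha 0.10 in the power section and 0.05 in the analysis section is a separate matter.

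**Conclusion.** The concern holds. For recurrence, the outcome that fixed the size of the trial, 103 patients in total do not provide 80% power against a 10-point margin. Power is about 46% if both true rates are 25%, and 10% under the plan's own projection. The matching two-arm size is 340, about 3.3 times the stated total (340 / 103).

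These figures assume 1:1 allocation, no losses and a Wald test of the risk difference at one-sided 0.10. In the sensitivity scenarios tried, neither a common rate between 15% and 35%, nor a true 5-point advantage for 4 days, nor reading 103 as per arm brings power to 80%. That the number came from a one-sample calculation is likely but unproven, and the conclusion does not need it.

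**What to change.** Rewrite the Power analysis paragraph:

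- Replace the 25% versus 35% scenario with 25% in both arms and a 10-point margin. If 35% was meant only to express the margin, say so.
- State that 103 patients give about 46% power for recurrence at one-sided alpha 0.10, or about 22% if the margin is judged by a two-sided 95% interval.
- Give the matching two-arm size: 170 per arm, 340 in total, before any allowance for dropout.
- State the allocation ratio and the formula or test used.
- If the total stays at 103, say that 80% power for recurrence applies only to a margin of about 18 points, and that the trial is exploratory for recurrence at 10 points.

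The cost is one paragraph and a less favourable power figure. Restating it needs no extra patients. It corrects the record but leaves the risk of an inconclusive result. Removing that risk would take about 340 patients, or a wider margin that the sponsor can justify clinically.

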Study Flow & Stop Criteria: The trial will be reported in accordance with the recommendations of the CONSORT Statement [28]. IRB approval will be obtained. All subjects or their legally authorized representative will provide written consent for study participation. The trial is registered with the US National Institutes of Health (ClinicalTrials.gov Identifier NCT01994980).

Screening will occur daily by study personnel. Eligible patients will be approached as soon as possible after inclusion criteria are met (i.e., 1-3 days prior to randomization). Randomization will occur using a computer-generated block pattern on the morning following the fourth day of appropriate antibiotic therapy.

Empiric antibiotic therapy will be instituted as soon as possible following BAL acquisition. The default antibiotic will be ceftriaxone 2 gram IV q24 hours. Patients with potential allergies to cephalosporins will receive levofloxacin 750 mg IV q24hours. Pre-existing treatment for a non-

pulmonary infection with at least one antibiotic that has appropriate activity against the VAP pathogen may be substituted for the default antibiotic. Once sensitivity data become available (approximately 72 hours after BAL acquisition), therapy may be de-escalated to a more narrow-spectrum agent (e.g., cefazolin) as indicated.

The default duration of antibiotic therapy will be determined by study group assignment; the treatment team will be asked to adhere to study group assignment whenever possible. However, the treatment team may choose to extend the duration of antibiotic therapy based on clinical circumstances, such as deterioration in hemodynamic or respiratory status that is believed to be related to incompletely treated VAP, or continued treatment of a non-pulmonary infection. The treatment team may also decide to extend the duration of antibiotic therapy based on the results of serial procalcitonin measurements. Finally, the treatment team may decide to extend the duration of antibiotic therapy based on the results of the BAL obtained the day after completion of therapy. These clinical decisions will take precedence over study group assignment.

Patients will be followed for 28 days or until hospital discharge, whichever occurs first. Please see attached data collection tool for detailed information.

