Kolmogorov-Smirnov test. Differences in the means of continuous variables that are distributed normally will be assessed using the Student's t-test. Differences in the medians of continuous variables that are not distributed normally will be assessed using the Wilcoxon Rank Test. Proportions of categorical variables will be compared using the chi-squared test. When expected cell counts are < 5, Fischer's exact test will be used. Univariate analysis of categorical outcomes will be expressed as the relative risk with 95% confidence intervals. A logistic regression model will be fit to address possible confounding by differences in baseline parameters between groups. Baseline variables associated with randomization status at the $p<0.25$ level by univariate analysis will be added to the model using a forward selection method. The overall contribution of the fitted model to predicting variability in the outcome of interest will be assessed using the likelihood ratio chi-squared test. The independent contribution of individual variables will be assessed using the Wald chi-squared test. Model fit was will be assessed using the Hosmer-Lemeshow goodness-of-fit chi-squared statistic, with $p>0.05$ indicating acceptable model calibration. The alpha error level is defined at 0.05, with statistical significance set at $p<0.05$.

Adverse Event Monitoring and Reporting: Adverse event monitoring will occur daily. The safety of the study will be monitored by an independent, external Data Safety Monitoring Board, consisting of a medical intensivist, and an infectious disease physician. The committee will meet biannually and submit written reports to the IRB.

References:

1. Edwards, J.R., K.D. Peterson, Y. Mu, S. Banerjee, K. Allen-Bridson, G. Morrell, et al., National Healthcare Safety Network (NHSN) report: data summary for 2006 through 2008, issued December 2009. *Am J Infect Control* 2009;37:783-805
2. Neu, H.C., The crisis in antibiotic resistance. *Science* 1992;257:1064-73
3. Mahgoub, S., J. Ahmed, and A.E. Glatt, Completely resistant *Acinetobacter baumannii* strains. *Infect Control Hosp Epidemiol* 2002;23:477-9
4. Kollef, M.H. and V.J. Fraser, Antibiotic resistance in the intensive care unit. *Ann Intern Med* 2001;134:298-314
5. Bradley, J.S., R. Guidos, S. Baragona, J.G. Bartlett, E. Rubinstein, G.G. Zhanel, et al., Anti-infective research and development--problems, challenges, and solutions. *Lancet Infect Dis* 2007;7:68-78

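### Antibiotic exposure is a main outcome, but the plan gives no estimate or confidence interval for the days saved, and its median summary can read 4 vs 8 across very different mean savings

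*Combined protocol and SAP*

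**What the plan says.** The Outcomes section states: "The two main outcomes will be effectiveness of treatment and antibiotic exposure". The hypothesis at the end of the Background is that 4 days "is equally effective and results in decreased antibiotic exposure among surgical ICU patients with early VAP". The measures are named under Additional Outcomes: "Days of antibiotics, antibiotic days (defined as the product of days of antibiotics and number of antibiotics per day". No counting period is given there.

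Under Study Flow & Stop Criteria, randomization takes place "on the morning following the fourth day of appropriate antibiotic therapy". After that, "the treatment team may choose to extend the duration of antibiotic therapy based on clinical circumstances"; procalcitonin results and the repeat lavage culture are further permitted reasons. These decisions override assignment, and they are open to both arms. The Data Analysis paragraph keeps extended patients in their assigned group.

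That paragraph sets the summary as "Data will be expressed as median (range) or number" (%). Continuous variables that pass a Kolmogorov-Smirnov check get a t-test. For the rest: "Differences in the medians of continuous variables that are not distributed normally will be assessed using the Wilcoxon Rank Test". The only intervals are for categorical outcomes: "Univariate analysis of categorical outcomes will be expressed as the relative risk with 95% confidence intervals".

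**The concern.** The benefit claimed for the shorter course is less antibiotic. A reader must weigh that benefit against recurrence, which the power analysis projects at 35% after 4 days against 25% before. That weighing needs the number of days saved and its precision, and the plan provides neither.

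The median suits this variable badly. Every patient has already had 4 days when randomized, so index-course days in the 4-day arm cannot fall below 4 and sit exactly at 4 for anyone not extended. The median stays there until about half the arm is extended, however long the extensions are. The Wilcoxon test compares whole distributions by rank, so it can be strongly significant when the medians are equal and non-significant when they differ by 4 days. Calling it a test of medians invites readers to attach its p-value to the wrong quantity.

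**Working it through.** **Plan's own figure.** None exists for exposure: no expected difference, standard deviation or sample size is stated. The total of 103 was derived for recurrence. It is used here only to set arm sizes of 51 and 52, assuming equal allocation (the ratio is not stated). Whether 103 is right is a separate matter.

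**Which test applies.** A 4-day arm with 38 patients at 4 days and 13 at 8 gives a Kolmogorov-Smirnov p of about 1e-10. Index-course days would therefore go to the Wilcoxon branch.

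**When the medians read 4 vs 8.** With 51 patients the median is the 26th ordered value, so it stays at 4 with up to 25 extended (25/51 = 49%). The 8-day median stays at 8 if fewer than half of that arm is extended and fewer than half stops early.

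**Mean saving (8-day mean minus 4-day mean).** Let a fraction f of the 4-day arm be extended to L days and a fraction g of the 8-day arm to 12 days:

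saving = [8(1 − g) + 12g] − [4(1 − f) + L·f]

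The values of f, g and L are assumptions. The results below use whole patients.

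| 4-day arm extended | 8-day arm extended | Medians | Mean saving (days) | Wilcoxon p |
|---|---|---|---|---|
| 20% (10/51) to 8 | none | 4 vs 8 | 3.2 | 1e-16 |
| 45% (23/51) to 8 | none | 4 vs 8 | 2.2 | 5e-10 |
| 30% (15/51) to 12 | none | 4 vs 8 | 1.6 | 7e-5 |
| 45% (23/51) to 12 | none | 4 vs 8 | 0.4 | 0.35 |
| 45% (23/51) to 12 | 20% (10/52) to 12 | 4 vs 8 | 1.2 | 0.09 |
| 45% (23/51) to 12 | 45% (23/52) to 12 | 4 vs 8 | 2.2 | 0.005 |
| 55% (28/51) to 8 | none | 8 vs 8 | 1.8 | 5e-8 |

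**Fourth row in full.** The 4-day mean is (28 × 4 + 23 × 12)/51 = 388/51 = 7.61, so the saving is 8 − 7.61 = 0.39. The standard deviation is 8 × √[(28 × 23/51²) × 51/50] = 4.02, and the standard error is 4.02/√51 = 0.563. The 8-day arm has no spread in this scenario. With t = 2.009 on 50 degrees of freedom, the 95% interval is 0.39 ± 1.13, or −0.7 to 1.5 days.

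**Same medians and nearly the same mean, different p.** The second and sixth rows both show medians of 4 vs 8 and a mean saving of about 2.2 days, with p-values of 5e-10 and 0.005. Neither the medians nor the p-value gives the size of the saving.

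**Counting window.** Counting from randomization removes the same 4 days from every patient. The nominal contrast becomes about 0 vs 4, and the mean difference in index-course days is unchanged. Including re-treatment can change it: at the projected recurrence rates, and assuming 8 days per recurrence, (0.35 − 0.25) × 8 = 0.8 day of the saving is lost.

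**The case against.** The strongest reply is that the planned output would not mislead on whether exposure fell. In the 0.4-day scenario the report would read 4 (4–12) vs 8 (8–8) with p = 0.35, so the extensions show in the range and the plan's own test would not support a claim of reduced exposure. In the 55% scenario the equal medians would appear beside p = 5e-8, so the saving is not hidden either. This stands. A reader might infer that the plan could declare a benefit when almost nothing was saved; the documents do not support that. What is missing is the size of the saving and its precision.

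A reader might also infer that the result reads 4 vs 8 whatever the true saving. That goes too far, for three reasons. It needs the 8-day median to stay at 8, and the same reasons for extension apply to that arm. Extension in both arms also restores part of the saving, as the fifth and sixth rows show. Finally, it applies to index-course days only: antibiotic days (days times number of drugs), or totals that include treatment of other infections, need not pile up at 4 and 8.

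Nor is the rank test the only planned test, since the t-test branch exists. Index-course days would hardly ever reach it, and it carries no planned interval.

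On the window, the plan refers to an attached data collection tool that is not in the available text. It may define what is counted, so the most that can be said is that the available text does not.

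**Conclusion.** The point holds in this limited form. For a main outcome, the plan gives no effect estimate and no confidence interval, and it misdescribes the Wilcoxon test. For index-course days, medians of 4 vs 8 are compatible with mean savings from 3.2 days down to 0.4 day in the scenarios examined, and medians of 8 vs 8 with a saving of 1.8 days. These figures rest on arms of 51 and 52 and on assumed extension rates and lengths. They show what the summary can conceal; they do not predict what the trial will find.

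The absence of an estimate and the wrong description of the test depend on none of these assumptions, and they apply equally to antibiotic days. This should be corrected, but it does not invalidate the design.

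**What to change.** 1. For days of antibiotics and antibiotic days, report the mean per patient in each arm and the difference (4-day minus 8-day, so a saving is negative) with a 95% confidence interval, by Welch or bootstrap.
2. Report the percentage of each arm that exceeded its assigned duration.
3. Keep the median (range) and the Wilcoxon test as supportive, and delete the statement that the test compares medians.
4. Make the main exposure measure all systemic antibiotic days, for any indication, from randomization to day 28 or hospital discharge, whichever comes first. Extensions and re-treatment of recurrences then count. Report index-course days separately, and state that the nominal contrast on the main measure is about 0 vs 4 days.
5. Confirm that the data collection tool records antibiotics given after the index course.

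The cost is plan wording and slightly more analysis, provided the tool already captures later antibiotics. Treatment, sample size and visits do not change. The stated saving may come out smaller than the medians would suggest.
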